## Design

The study design of the impact evaluation is a cross-sectional stepped-wedge cluster randomised controlled trial, where the timing of implementation is staggered across local authorities. The point at which local authorities begin implementing the intervention is selected at random, constrained by their level of readiness to implement the model. In this way, all the local authorities in the sample will eventually implement the Family Safeguarding model, but randomising the start date of the implementation of Family Safeguarding will allow service users in the local authorities that have not yet implemented the programme to act as a control group against service in local authorities where Family Safeguarding has already been implemented.

Given that, prior to the evaluation, there was already an existing need to stagger roll-outs over time, this means that nobody will be denied a service that they might otherwise have received. Local authorities implementing on different timescales will also allow us to take time-based effects into account, with every local authority also acting as a control group for itself over time.

RCT Design Table		
Trial type and number of arms		Stepped wedge cluster randomised controlled trial, two arms
Unit of randomisation		Local authority
Stratification variables		Low/High readiness to implement
Primary outcome	variable	Whether or not the child has become looked after
	measure	Coded 1 if the child has become looked after at any point within 18 months of the referral. Coded 0 if the child has not become looked after within this period.
	sample	Children aged 0-12 that have been referred within the trial period.

Secondary outcome 1	variable	Whether or not the child has returned to statutory services, following a CPP
	measure	Coded 1 if the child finishes a CPP and then returns to statutory services (i.e. begins a new CPP, CIN plan or becomes CLA) within 36 months of the referral start date, coded 0 if they have not re-entered statutory services within this time period.
	sample	Children aged 0-12 that have been referred within the trial period without them going into care.
Secondary outcome 2	variable	CPP plan duration
	measure	Discrete variable equal to the number of days that the child has been on a single CPP. Plan length is recorded up to 24 months from the start of the CPP and censored for larger values.

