	sample	Children aged 0-12 that have been referred within the trial period and that also started a CPP plan within 12 months of the initial referral start date.
Secondary outcome 3	variable	Days on CPPs
	measure	Discrete variable equal to the number of days that the child has been on CPP plans over a period of 36 months from initial referral.
	sample	Children aged 0-12 that have been referred within the trial period.
Secondary outcome 4	variable	Whether or not the child proceeds to care proceedings
	measure	Coded 1 if the child has started care proceedings following pre-proceedings (under the PLO) within 16 weeks of the first pre-proceedings meeting, and coded 0 if not.
	sample	Children aged 0-12 that have been referred within the trial period and that started pre-proceedings within 18 months of the referral.
Secondary outcome 5	variable	Repeat referrals for parental substance misuse, parental mental health or domestic violence
	measure	Coded 1 if the child has been re-referred within 18 months of an initial referral where the factors identified at the end of assessment included either parental substance misuse, parental mental health, or domestic violence. As measured 18 months after first referral. Coded 0 if not re-referred within 18 months.
	sample	Children aged 0-12 that have been referred within the trial period. The factors identified at assessment must include parental substance misuse, domestic violence, or parental mental health.

Secondary outcome 6	variable	Unauthorised school absence rates
	measure	Continuous variable equal to the percentage of sessions missed due to unauthorised absence out of all the school sessions the child was expected to attend for the three terms that start after the initial referral date.
	sample	Children aged 0-12 that have been referred within the trial period.

We will use administrative, secondary data for the analysis. The administrative data will be provided by each local authority in the evaluation. Local authorities that are participating in the evaluation have committed to providing data. For details please see the Data Gathering section below.

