#### **Whether or not the child has returned to statutory services, following a CPP**

To answer research question 2, we use a binary outcome measure, indicating whether or not the child has returned to statutory services within 36 months of the initial referral start date, having had a CPP closed following the initial referral start date. Our sample will include any child aged 0-12 that has had a referral within the trial period.

This outcome will seek to act as a measure for the quality of assessment and direct work with children and their families. We choose return to statutory services (rather than considering CPPs only) as our outcome measure to avoid classifying children whose needs have escalated to e.g. going into foster care as "non-returners". We acknowledge that we do count children that stay on CPPs as non-returners. If implementing Family Safeguarding changes the allocation of children to CIN and CP plans, this will further affect the measure. Thus care must be taken interpreting this outcome measure.

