### **Repeat referrals for domestic violence, mental health or substance misuse**

To answer research question 5, the outcome measure is a binary variable of whether or not a child that has previously been referred for parental substance misuse, domestic violence, or parental mental health has been re-referred to children's social care within 18 months of the initial referral start date. Our sample will be restricted to children aged 0-12 at the time of referral who have been referred within the trial period and whose initial assessment identified parental substance misuse, domestic violence, or parental mental health as factors identified at the end of assessment. Since these factors are only identified at assessment, our sample

---

 Note that this does not include cases that lead directly to a Multi Agency Risk Assessment Conference (MARAC).

is restricted to children whose referral has progressed to an assessment and where one of the factors identified at assessment includes one of the three factors defined above.

Since a key element of Family Safeguarding is the inclusion of specialist adult practitioners with domestic abuse, mental health and substance misuse expertise, this analysis will allow us to evaluate one of the main components of the Family Safeguarding programme more closely.

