### **Unauthorised school absence rates**

To answer research question 6, the outcome measure is a continuous variable measuring the percentage of sessions missed by a child within our analytical sample due to unauthorised absence, out of all sessions the child was expected to attend. We will measure the school attendance rate of three consecutive school terms, beginning with the closest school term beginning after the start of the period in which the child entered our sample. This will involve having up to three measurements per young person.

Unauthorised school absence rates are a valuable addition to the children's social care outcome measures detailed above as they directly relate to children's opportunities and outcomes outside of children's social care. Since there exists no direct link in the logic model between the model and unauthorised school absence rates, this outcome is of an exploratory nature to see whether we can capture part of the potential wider benefits of Family Safeguarding.

Care should be taken in the interpretation of the results of our analysis. Each result (pertaining to a specific outcome measure) will help create a picture of the changes that are taking place because of the intervention. However, in isolation we should be wary of concluding strongly that one direction is good or bad. This is especially true in terms of our measures relating to research questions 2 and 3. For example, a reduction in the length of CPPs could be positive - indicating that children's social care interventions address the families needs more rapidly. However, it could also be negative - and indicative instead of cases being closed prematurely, with families having unmet needs which could lead them to return to statutory services shortly after closing the case. Thus we will evaluate each analysis in the context of the others that we conduct. We will also interpret the results alongside the findings of the associated implementation and process evaluation, which may shed further light on the factors driving these outcome changes. We will also reflect any remaining ambiguity accordingly in our reports.

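### Secondary outcome 5 scores children in care or with a case still open as not re-referred when no second referral is recorded, so a difference may partly reflect unequal opportunity for re-referral

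*Protocol*

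**What the plan says.** All references are to the protocol. The RCT Design Table (Design section) codes SO5 as 1 for a re-referral within 18 months of the index referral, and closes the rule with "As measured 18 months after first referral. Coded 0 if not re-referred within 18 months". Beyond age and referral date, the sample has one restriction: "The factors identified at assessment must include parental substance misuse, domestic violence, or parental mental health". The narrative under Outcome measures repeats the definition ("has been re-referred to children's social care within 18 months of the initial referral start date"), and that section says the table governs if the two differ. A footnote there adds that cases need not be open after assessment. The Conditions section moves the SO5 index date to the first trial-period referral whose assessment found one of the three factors.

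The Secondary Analysis section gives SO5 the same logistic model as the primary outcome. Neither that section nor the Sensitivity Analysis and Regression specifications sections deals with care entry or still-open cases for SO5.

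Secondary outcome 1 (SO1, return after a child protection plan) is treated differently. Becoming looked after counts as a return, and the reason given is "to avoid classifying children whose needs have escalated to e.g. going into foster care as" non-returners. For children still on a plan the narrative says: "We acknowledge that we do count children that stay on CPPs as non-returners". At the end of Outcome measures there is a general caution against reading any single result in isolation, with the emphasis "This is especially true in terms of our measures relating to research questions 2 and 3". SO5 answers research question 5.

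**The concern.** A zero on SO5 can mean three things: the case closed and the family did not come back; the child went into care; or the case was never closed. Only the first is what research question 5 is about. In the other two, the child may have had little or no chance of a new referral.

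Both could differ by condition. Care entry is what the programme mainly aims to change. The Days on CPPs section says that longer plans could mean more support or unmet need, and footnote 37 in the IPE Design Table records uncertainty about the effect on plan length. If cases are held longer, SO5 falls with no real benefit. If fewer children enter care, more remain exposed to re-referral and SO5 can rise although the programme is working. The outcome is meant to look closely at the specialist adult practitioners, one of the programme's main components, so an ambiguous result here would matter.

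**Working it through.** **1. The protocol's own figure.** The only stated detectable difference is 0.0105, for the primary outcome. Inputs from the power table and Appendix B: 5 authorities, 6 periods, m = 1,700 per cell, p = 0.06, ICC 0.00722, two-sided alpha 0.05, power 0.80. Total 5 × 6 × 1,700 = 51,000, as stated.

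Hussey-Hughes variance: I·s²(s² + Tτ²) / [(IU − W)s² + (U² + ITU − TW − IV)τ²], with I = 5, T = 6, U = 15, W = V = 55.
- s² = 0.0564 × 0.99278 / 1,700 = 3.294 × 10⁻⁵
- τ² = 0.0564 × 0.00722 = 4.072 × 10⁻⁴
- SE = 0.003739; detectable difference = (1.960 + 0.842) × 0.003739 = 0.0105

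The figure reproduces. It belongs to the primary outcome, and no counterpart is given for SO5.

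**2. Longer case-holding.** Assumptions, none of them from the protocol: re-referral r over 18 months (548 days); every case open for *o* days; no re-referral recorded while open; constant hazard after closure. Then h = −ln(1 − r)/(548 − o). With *d* extra open days, the SO5 rate is 1 − exp[−h(548 − o − d)].

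| r | o | d | SO5 rate | Fall (points) |
|---|---|---|---|---|
| 20% | 120 | 30 | 18.74% | 1.26 |
| 20% | 180 | 30 | 18.53% | 1.47 |
| 20% | 120 | 60 | 17.46% | 2.54 |
| 20% | 180 | 60 | 17.04% | 2.96 |
| 15% | 120 to 180 | 30 | – | 0.97 to 1.13 |
| 25% | 120 to 180 | 30 | – | 1.53 to 1.78 |

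Thirty extra open days therefore lower SO5 by about 1.0 to 1.8 points while the underlying hazard is unchanged.

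**3. Care entry alone.** Let *s* be the share never at risk of a recorded re-referral and *r* the risk in the rest, so the SO5 rate is (1 − s)·r. A change in *s* of 1.05 points, the size of the primary detectable difference, moves SO5 by 1.05 × 0.15 = 0.16 to 1.05 × 0.35 = 0.37 points (r assumed 15-35%). SO5 falls if care entry rises, and rises if care entry falls.

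**4. What a reversed sign would need.** If *r* worsens by 10% in relative terms, SO5 still appears to improve once *s* exceeds 1 − (1 − s₀)/1.10. From s₀ = 6% that is a rise of 8.6 points; from s₀ = 30%, 6.4 points. Example: *s* from 10% to 25% and *r* from 25% to 27% gives 0.90 × 0.25 = 22.5% against 0.75 × 0.27 = 20.3%.

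**5. Scale for SO5.** Using the formula in step 1 with m set to 30-70% of 1,700, an SO5 rate of 12-30% and the same ICC (all assumed), the SO5 detectable difference is about 1.7 to 3.7 points.

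**The case against.** The strongest reply is that the mechanism rests on an assumption. The protocol never defines re-referral and never says that an open or looked-after case cannot generate one. A child re-referred before entering care scores 1. A reader might infer that every child who enters care is scored as not re-referred, or that the planning 6% are; the documents support neither. The 6% is a whole-population proxy from published annual figures, not an SO5 rate. This stands. The point applies only to children with no recorded second referral.

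Second, the general caution covers every outcome, and care entry is reported as the primary outcome. This softens the problem. But the caution singles out research questions 2 and 3, and the primary outcome covers a wider sample whose 18-month clock can start at an earlier referral. It does not show care entry within the SO5 sample.

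Third, the protocol does not say that cases will be held longer. Plan time is not open-case time, and some SO5 cases close at assessment, so 30 extra days on average has no source in the document. This also stands: the figures illustrate sensitivity and do not forecast.

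Fourth, recoding SO5 as re-referral or care would change research question 5, overlap the primary outcome and leave still-open cases at 0. SO1 is not an exact precedent either. There, care counts only after a plan has ended, the table's sample is "Children aged 0-12 that have been referred within the trial period without them going into care", and children still on a plan are knowingly accepted as non-returners. So the composite belongs in a sensitivity analysis.

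**Conclusion.** The point holds in a limited form. SO5 as coded mixes re-referral with the opportunity for re-referral, and the protocol has no SO5-specific rule, analysis or caveat for this, although it saw the same problem for SO1. The effect can run either way.

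Care entry by itself is a small route, about 0.2 to 0.4 points at the primary detectable difference. Longer or shorter case-holding is the larger one, about 1.0 to 1.8 points per 30 days. Both sizes rest on assumed re-referral rates and on referrals being recorded only when no case is open; the second also rests on assumed open time and a constant hazard.

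Two stronger readings are tempting. One is that the artefact matches the effect the trial is powered for. The 1.05 points belong to the primary outcome; against an assumed SO5 range of 1.7 to 3.7 points, the 30-day shift is mostly smaller. The other is that research question 5 will be answered in the wrong direction. That is arithmetically possible, but in the scenarios worked above it takes a rise of more than 6 points in the share never at risk, and nothing in the protocol makes such a rise likely. The protocol also does not call a lower SO5 rate a success, although that is the natural reading of the question.

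**What to change.** - Keep the stated coding as the main SO5 analysis. State in the RCT Design Table whether a referral received on an open or looked-after case counts as a re-referral.
- Add one pre-specified sensitivity analysis: code 1 if the child is re-referred or becomes looked after within 18 months of the SO5 index referral.
- Report by condition, for the SO5 sample: the share looked after within 18 months, the share whose case never closed by 18 months, and days with no open case.
- State that research question 5 will be interpreted only alongside these figures.
- If re-referral per day after closure is shown, label it descriptive. Closure happens after allocation and may be affected by it; footnote 4 gives the same reason for not starting the SO1 clock at the end of a plan.

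The cost is a few lines of wording and a little extra analysis. Care-entry dates are already needed for the primary outcome. Open-referral time is already needed for the alternative treatment definitions, but only within the trial period, so closure dates up to 18 months after the index referral must also be requested for late entrants. The change can be made before outcome data are obtained.

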## Participants

The children that we include in our sample are those who meet the following criteria.

- They are referred to the local authorities' children's services. This is a rather broad baseline population which we use because the implementation of Family Safeguarding can potentially lead to changes in assessment thresholds.
- Their original referral date falls within the trial period as defined above.
- Are aged 0-12 at the time of referral. This is the primary age group that the Family Safeguarding teams in the developer local authority Hertfordshire work with. While Safeguarding teams can in theory work with adolescents as well, safeguarding concerns among adolescents are more likely to become contextual which in some local authorities are specifically addressed by adolescent teams. Since the Family Safeguarding model also focuses on work with parents, the implementation is likely to have a larger effect on children up to the age of 12 than on young people.

This will provide our analytical sample, which will then be further restricted or extended for different outcomes, as described in the RCT Design Table above and in the 'Outcome measures' section below.

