## Conditions

Children that form part of the samples described above will be designated as part of the treatment and control groups according to whether Family Safeguarding was implemented in their local authority at the time of their first referral start date in the trial period. This date also marks the starting point from which we measure any outcomes over the periods of time defined in the RCT Design Table above. Compared to other possible dates at a later stage in the referral, this constitutes a conservative approach. Some children in the control group might have been in contact with Family Safeguarding teams at a later stage of their referral which can bias our estimate downwards. We revisit this approach in our sensitivity analysis.

We only consider referrals that started during or after our baseline period and do not allow children to enter our sample twice i.e. any additional referrals after the first referral in the trial period defining our baseline population will not lead to additional entry into the sample, though the consequences of subsequent referrals may affect the outcome coding.

For Secondary Outcome 5 - Repeat referrals for domestic violence, mental health or substance misuse - we alter our definition of treatment and control. Here, the relevant referral date will be the first referral in the trial period, where the following assessment identified one of the three factors at the end of assessment. This is because some activities of Family Safeguarding such as specialist adult practitioners only focus on children in this subgroup. Thus, any referrals prior to this, where the assessment following a referral did not identify one of these factors at the end of assessment, will be disregarded.

Conditions Table		
Condition	Primary Outcome and Secondary Outcomes 1-4 & 6 definition	Secondary Outcome 5 definition
Control	Children whose first referral in the trial period took place when the local authority was running their business as usual model.	Children whose first referral in the trial period - where the factors identified at the end of assessment included either parental substance misuse, parental mental health, or domestic violence - took place when the local authority was running their business as usual model.

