#### **CPP plan duration**

To answer research question 3, we use two different models. First, we will use a discrete variable measuring the number of days that the child has been on a single CPP, over a period of 24 months from the start of the CPP and censored for larger values. Our sample

---

 Note that the episode of care does not have to result directly from the initial referral, e.g. a child who had a case that was closed but then returns to children's services and becomes looked after within 24 months of the initial referral date will be coded as 1.

 We use the referral start date as the starting point for the 24 months time frame (as opposed to imposing a time frame starting from the end of the first CPP) to reduce potential endogeneity through selection into the sample. Endogeneity can occur if social workers assess risk differently through Family Safeguarding. This might lead to a change in the length of CPPs, which in turn can result in different children in treatment and control groups terminating a first CPP within the trial period.

 that is, any values over 24 months will be coded as 24 months.

will include any child aged 0-12 that has had a referral within the trial period that led to a child protection plan (CPP) within 12 months of the referral start date.

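### Secondary outcomes 4 and 5 (and, less importantly, 2) are analysed only in children selected by a post-referral event that Family Safeguarding may alter, so their treated and control samples cannot be assumed comparable

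*Protocol*

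**What the plan says.** The Conditions section assigns a child to treatment or control by whether the local authority had implemented Family Safeguarding at the child's first referral in the trial period. For three secondary outcomes the RCT Design Table then adds a requirement that can only be met later:

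- Outcome 2 (CPP plan duration): children "that also started a CPP plan within 12 months of the initial referral start date".
- Outcome 4 (care proceedings within 16 weeks of the first pre-proceedings meeting): children "that started pre-proceedings within 18 months of the referral".
- Outcome 5 (re-referral within 18 months): "The factors identified at assessment must include parental substance misuse, domestic violence, or parental mental health". The Outcome measures text adds that the sample "is restricted to children whose referral has progressed to an assessment". The Conditions section also dates exposure differently for this outcome: "Here, the relevant referral date will be the first referral in the trial period, where the following assessment identified one of the three factors". Earlier referrals without such a factor are ignored.

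The protocol recognises the selection problem elsewhere. On taking all referrals as the base population, the Participants section says: "This is a rather broad baseline population which we use because the implementation of Family Safeguarding can potentially lead to changes in assessment thresholds". Footnote 4, which concerns outcome 1, starts the clock at referral "to reduce potential endogeneity through selection into the sample", because social workers may assess risk differently under the model. The text on outcome 1 accepts that allocation to CIN and CP plans may shift, and the Risks table lists changed assessment thresholds as a possible source of bias. Secondary Analysis applies the primary regression to the binary outcomes and has no step for selection into a restricted sample.

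**The concern.** Each entry event happens after treatment status is set, and each is a decision or a record made by staff working under the model or under business as usual. Randomising the rollout order protects a comparison of all referred children. It does not protect a comparison of those who later meet a condition that the intervention may influence.

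For outcome 5 the link is close. The model brings in specialists in domestic abuse, mental health and substance misuse, the same three factors that decide entry. Footnote 31 lists a thresholds workshop for all staff, including those in assessment services. For outcome 4, a model meant to keep families together may change which families reach pre-proceedings, and a child taken straight to care proceedings is never in the sample.

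The Outcome measures section uses outcome 4 to judge whether the effect is strongest at the edge of care, and outcome 5 to look closely at the specialist component. Research questions 4 and 5 ask about impact. If case mix at entry moves, either outcome could suggest benefit or harm that no child experienced.

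**Working it through.** **The plan's own figure.** The only power figure is the MDES for the primary outcome, 0.0105. Inputs from the sample size table and Appendix B: I = 5 clusters, T = 6 periods, 1,700 children per cell, ICC 0.00722, baseline 0.06, two-sided alpha 0.05, power 0.80. The Hussey-Hughes variance for a complete stepped wedge, with total variance 0.06 × 0.94, gives an MDES of 2.80 × SE = 0.01048, which agrees. The sample is 5 × 6 × 1,700 = 51,000. These figures concern all referred children and are not in question. No figure is given for outcomes 2, 4 or 5.

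**Side by side.**

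| Outcome | Entry event | When | Full-sample companion |
|---|---|---|---|
| 2 | CPP started | up to 12 months after referral | outcome 3 |
| 4 | pre-proceedings started | up to 18 months after referral | none |
| 5 | one of three factors recorded | at the assessment after referral | none |

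**Illustration 1: no effect on any child, only entry changes.** All rates are assumed. The control sample has two equal risk strata with values H and L. A fraction x of lower-risk children is diverted from entry (outcomes 2 and 4) or added to it (outcome 5).

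- Diverted: treated value = [H + L(1 - x)] / (2 - x). Added: treated value = [H + L(1 + x)] / (2 + x). Control value = (H + L)/2.
- Outcome 4, H = 60%, L = 20%, control 40%. x = 10%: 0.78/1.9 = 41.1% (+1.1 points). x = 30%: 0.74/1.7 = 43.5% (+3.5). x = 50%: 0.70/1.5 = 46.7% (+6.7).
- Outcome 5, H = 30%, L = 20%, control 25%. x = 10%: 0.52/2.1 = 24.8% (-0.2 points). x = 30%: 0.56/2.3 = 24.3% (-0.7). x = 50%: 0.60/2.5 = 24.0% (-1.0).
- Outcome 2, H = 300 days, L = 150 days, control 225. x = 10%: 435/1.9 = 228.9 (+3.9 days). x = 30%: 405/1.7 = 238.2 (+13.2). x = 50%: 375/1.5 = 250.0 (+25.0).
- With x = 0, every difference is 0.

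**Illustration 2: sharper contrasts, again assumed.**

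- Outcome 4: of 100 control children entering pre-proceedings, 50 go on to proceedings. Suppose 25 children at 20% risk are kept out of both. Then (50 - 5)/75 = 60%, an apparent 10-point harm, although proceedings fell from 50 to 45. If the diverted risk is 0%, 50/75 = 66.7%. If it is 50%, the sample average, 37.5/75 = 50% and there is no distortion.
- Outcome 5: control re-referral is 25 in 100. Recording factors in 10 more children at 10% risk gives 26/110 = 23.6%. Recording them in 30 more gives 28/130 = 21.5%.

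The sign in these examples depends on the children lost or gained being at lower risk than the rest.

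**Treatment assignment in outcome 5.** Take a child first referred before go-live with no factor recorded, then referred after go-live with one recorded. Under the Conditions section this child is a control for every other outcome for which the child qualifies, but treated for outcome 5. Here the recorded factor decides both entry and condition.

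**What a full-sample version shows.** In the outcome 4 example, proceedings counted over all referred children fall from 50 to 45 on an unchanged denominator, a 10% relative fall in the right direction.

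**The case against.** The restrictions are deliberate. Research question 4 asks about progression from pre-proceedings. The Outcome measures section explains that some families mainly meet the team at that stage, and the Conditions section says specialist work focuses on the subgroup in outcome 5. Proceedings or re-referrals among all referred children answer a different question and dilute an effect confined to the subgroup. This stands, and is why the restricted outcomes should not simply be replaced.

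For outcome 2, the plan already pairs it with outcome 3, which uses all referred children and codes those with no CPP as 0. It promises careful interpretation for research questions 2 and 3, and has the process evaluation examine plan length. This also stands, and makes outcome 2 the minor part of the point.

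For outcome 5, assessment may sit with teams separate from the specialists, and the documents give only the title of the thresholds workshop. That staff would record more, milder factors is conjecture. This weakens the mechanism without removing it, since assessment staff are among those trained.

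The model also includes covariates taken at referral, the primary outcome would catch many children who go straight into care, and the plan promises to read results together. These help, but none addresses unmeasured differences in who enters the restricted samples.

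A reader might infer that the samples are in fact not comparable, or that distortions of the illustrated size should be expected. The documents do not support this: they call threshold change possible and give no rates. A reader might also take outcome 1 as the place where the plan solved the problem. Its table sample is limited to children who did not go into care, which is also a post-referral condition, and the table takes precedence over the broader wording in the text.

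**Conclusion.** The point holds in limited form. Outcomes 4 and 5 are estimated only in children selected after treatment status is set, by events that the protocol's own reasoning says the model may affect. They have no full-sample companion and no explicit selection caveat. Outcome 5 has the added weakness that its condition is dated from the first referral with a recorded factor. Comparability cannot be assumed, and an apparent benefit or harm could come from a change in entry alone.

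The size is not known. It is zero if entry does not change, or if the children gained or lost carry average risk. The figures above (+1.1 to +6.7 points and, in the sharper case, 10 or more for outcome 4; -0.2 to -1.0 and, in the sharper case, -1.4 to -3.5 for outcome 5) rest wholly on assumed rates and show direction and possible scale only. Outcome 2 is largely covered by outcome 3. The primary outcome and outcomes 3 and 6 use all referred children and are untouched. Outcome 1's table sample needs a check of the same kind.

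**What to change.** 1. Keep outcomes 2, 4 and 5 as defined, but state that they are conditional on a post-referral event and are not unbiased effects of the model.
2. For each, report the share of referred children who enter the sample by condition, using the same regression as the primary outcome.
3. Add companions for outcomes 4 and 5 in all children aged 0-12 at first referral, with treatment set by the standard first-referral rule:
   - Outcome 4: care proceedings started within 18 months plus 16 weeks of first referral, with or without pre-proceedings.
   - Outcome 5: any re-referral within 18 months of first referral.
4. Base causal statements for research questions 4 and 5 on the companions, and let outcome 3 carry the causal answer to research question 3. State which versions enter the Hochberg family; those carrying causal statements belong in it.
5. Check the outcome 1 sample in the table against its text, and either remove the condition about going into care or treat it in the same way.

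The cost is protocol wording and a few more model runs. Outcome data are to be collected until 36 months after the trial period, which covers the longer window, and the sample size section already foresees a protocol update before outcome data are collected. There are two downsides. The full-sample versions dilute effects confined to the subgroup. The sponsor must also confirm that the data template captures care proceedings begun without pre-proceedings, because the protocol does not show this.
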